3.7. Setting

Screening and therapy sessions will either be conducted in: 1. AUC campuses (New Cairo and Downtown); or 2. Due to Cairo's significant size and transportation difficulties, to better accommodate our participants, we are in the process of establishing ties with private clinics located in areas such as Mohandessin and Zayed, which are far from the AUC campuses. If they show their willingness to cooperate and contribute to the project, we will utilize their facilities for the purpose of conducting therapy sessions if needed. This is also for heterogeneity and inclusiveness purposes, as we want to include participants from different backgrounds and from different socioeconomic urban settings i.e. different neighbourhood in Cairo.

3.8. Pilot study procedures

Recruitment & prescreening

Our sample will be recruited from multiple settings, including referrals from MHPs in private and public settings, social media outlets, via calls for participation through university announcements, and local NGOs.

Participant will be recruited using a convenience sampling strategy [69]. Given the sensitivity of this population exposed to violence and potentially associated stigma, convenience sampling might facilitate recruitment. More importantly convenience sampling is recommended in such exploratory projects to ensure flexibility needed to make ‘real-time judgements’ during fieldwork regarding changes needed in sample characteristics or size [70].

Participants will be contacted by the applicant for phone prescreening call. Ethical guidelines recommend that phone prescreening may be conducted to determine specific inclusion and exclusion criteria and is allowed before obtaining consent. We use phone screening, for the purpose of not wasting participant’s time, and given transportation difficulties in Cairo. During the phone screening call, participants will be:

- introduced to the researcher.
- told how long the phone call is expected to take.
- informed that a set of questions will be asked to determine eligibility of the nature and sensitivity of the questions.
- asked whether there might be a better time for them to answer these questions.
- If they agree to conduct the phone call at this moment or suggested another time to be re-contacted, they will be asked if they had experienced violence for a long period of time.
- pre-screened on the phone using the PCL-5, which consists of 20 PCL-5, a diagnostic tool with 20-items to assesses the symptoms of PTSD (See Section 3.10 Outcome measures). A score above 23 suggested a provisional diagnosis of PTSD in another Arabic-speaking sample [71]. No additional identifying information will be asked and no official record of scores will be kept or connected to the participant in anyway. The same procedure was conducted in another pilot study in a trauma-focused online therapy program in Egypt [72]. Participants who score over 23 will be sent the consent sheet via the contact information they provided and invited for a study information and screening session.

Screening & informed consent

Screening interviews will be conducted by the applicant (NH), who is also a psychotherapist and practices under the licence of Maadi Psychology Center in Cairo, Egypt. During this interview additional inclusion criteria questions (i.e., immediate risk of suicide, acute psychosis, severe alcohol, or drug abuse) will be asked. Additionally, participants will be asked if they have been in therapy before or are currently in therapy. If patients are not eligible or do not want to participate, they will be referred to other treatment pathways and public and private facilities in Cairo. We have provided a list of available and trusted service providers or facilities (emergency services and outpatient services; please see Appendix 6).

NH will then explain the study information in detail and respond to the participants’ questions. This part of the session will resemble an “onboarding session,” in which the content of the manual and the study procedures will be explained more in detail. They will be informed that if they participate in the study, they will receive a standardized group therapy following a manual that includes 18-25 sessions. They will be informed of the study design, and the difference between therapy sessions and assessment

and feedback sessions. Please see below sections of procedures details. They will also be notified that therapy is provided at no cost and that their time for feedback interviews will be compensated. (For more information on compensation, please see below). They will be informed about their voluntary participation and the possibility of withdrawal at any time.

If the participant still agrees to participate, they will be asked to sign the informed consent form. Please see Appendix 2 for consent forms. As per guidelines, the participant would have had time to read the consent form sent to them prior to coming to the screening session to have more than 24 hours before consenting. We will retain the consent form as part of the study records.

Participants will then be asked to fill self-report questionnaires. Please see Section 3.10 for outcome measures. Patients will be given the option to either complete the self-report questionnaires themselves, or, if they prefer to have the therapist read the items to them. If the participant screens positive for CPTSD using the ITQ. They will then be informed that they are eligible and asked to join our study. If they agree to join, we will collect socio-demographic data, i.e., sex, age, religion, marital status, education, occupation, income.

Participants will receive compensation of 700 EGP for this session.

Cultural module-ITI pilot

At the end of this interview, patients who have screened positive for CPTSD will be asked if they are interested in participating in two formulation sessions to pilot the ITI and the cultural and structural module (please see Section 3.5). This question will be asked to participants whether they are interested in joining our therapy program or not. These sessions will be conducted independently of the screening and therapy process. Participants will be informed that their decision will not impact their inclusion in the therapeutic program and will be reminded that they have the right to decline. They will be reminded about their voluntary participation and the possibility of withdrawal at any time. They will be given a separate consent sheet and will also be informed that their time will be compensated. Please see appendix 2 for consent forms.

NH will conduct the ITI (original version and additional items of the cultural and structural module), to assess the feasibility and cultural applicability of the added module. She will be trained along with the UniL team to conduct the clinical interview. ITI formulation sessions will be audio recorded for research purposes. We will record sessions to use them to collect idioms of distress, free-listed symptoms, and cultural norms as a part of the ethnopsychological portion of this study, which will allow us to further adapt the diagnostic module and the therapy in the future. We did not conduct interviews with patients during the formative research phase (only mental health professionals, and family members/close ones of individuals exposed to violence). This was due to the high vulnerability of our population, as it would have been unethical to cause distress through interview questions without providing a treatment option.

Participants will then be invited to a debriefing interview to provide us feedback on the ITI, including the module. Feedback interviews will be conducted by a (master-level) RA and will be audio-recorded. Please see Appendix 8 for sample patient feedback interview guide; provided are guides in English, once finalized guides will be translated in Arabic.

Participants will receive compensation of 700 EGP per session, for a total of three sessions (two ITI sessions and one feedback session).

Therapeutic program

The first three modules will be provided in a group, face-to-face setting in either AUC campus or other clinics (see Section 3.7). Due to clinical reasons, Module 4 (narrative exposure) needs to be delivered individually. Module 4 will take 5-7 sessions. Hence, due to budget constraints, only 5–10 participants will be chosen to complete the narrative exposure therapy component. We will ask participants if they are interested to conduct additional 4 sessions to enhance PTSD symptoms. We will ask one group at a time until the desired number is fulfilled.

It is expected that individuals who do not undergo the narrative exposure therapy module will still experience positive outcomes from the remaining components of the intervention, including improvements in symptoms of complex PTSD and overall functioning.

Participants will be divided into four groups. Each group will consist of five participants. Groups will be organized based on geographical preference of therapy and/or participant characteristics (e.g. gender or education level) to enhance group harmony and cohesiveness. Two psychotherapists, the applicant (who is a trained psychotherapist herself), and another psychotherapist, will be trained on using the manual and will lead group sessions. They will be assisted by two master-level psychotherapists in training. The graduate program committee in the counselling psychology program AUC agreed that two master's students could serve as co-facilitators as a part of their clinical internship.

Supervision: During the 18-week intervention, weekly preparatory and peer-supervision meetings will be held. In-training therapists will have weekly supervision with [name] from AUC faculty. The whole team will also receive supervision from an experienced psychiatrist and psychotherapist with over 10 years of clinical and supervision expertise in third-wave cognitive-behavioral therapy modalities in group and individual formats (twice a month). This supervision model and team triangulation method ensure the quality and appropriateness of the intervention, as well as the ethical conduct of the students throughout their participation.

Following each therapeutic module, participants will complete an assessment including all outcome measures (see Section 3.10). Assessments will be conducted by either therapists or co-facilitators. Participants will also participate in a short qualitative interview in group format to provide their feedback on each module of the manual. Feedback interviews will be conducted by graduate (master-level) RAs. Initial baseline assessments will be administered by NH, who possesses a Citi training certificate, during the months of July and August. The T1, T2, and T3 assessments, which will be carried out by an RA(s), will not commence until September 21st 2025. Recruitment of the RAs has not yet taken place; however, it is scheduled to occur within the next month. After the recruitment of the RA, they will complete the Citi training and subsequently provide their certificate to the IRB prior to commencing any assessment activities. Please see Appendix 8 for sample patient feedback interview guide for module 1 & 2; provided are guides in English, once finalized guides will be translated in Arabic. Feedback focus groups will be audio recorded. For each assessment and feedback session participants will receive 700 EGP as compensation.

Therapists and co-facilitators will fill out a fidelity check form after each session, to retain information regarding the implementation, process evaluation, and acceptability of the intervention. Please see Appendix 4 for the fidelity form. Based on these forms, RAs will then conduct debriefing focus group discussions with therapists and co-facilitators after each module. Feedback from patients and therapists, will be used to make final adaptations in the adapted ESTAIR manual.

Therapists and RAs costs are covered by the Prix CADOT funding. MA-level therapists in training cannot be paid as their work will count towards the hours they need to fulfill in their degree.

We provide below two tables with the weekly progression plans of the pilot study:

3 module plan:

Week	0	1	2-6	6	7-12	12	13-17	18	19
Visit	Study information & pre-assessment	Introduction session	Module 1	Intermediate assessment 1/Feedback	Module 2	Intermediate assessment 2/Feedback	Module 3	Final Session	Post-assessment/Feedback

4 module plan:

Week	0	1	2-6	6	7-12	12	13-17	17	18-24	25	26
Visit	Study information & pre-assessment	Introductory session	Module 1	Intermediate assessment 1/Feedback	Module 2	Intermediate assessment 2/Feedback	Module 3	Intermediate assessment 3/Feedback	Module 4 (individual therapy)	Final session	Post-assessment/Feedback

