3.4. Study intervention: Enhanced-STAIR

Results from the formative research, along with team discussions and decisions, were documented and are being used in adapting the ESTAIR manual. This includes all cultural adaptations, as well as adaptations to take structural factors into account. A template based on the RECAPT criteria will be used to record all adaptations throughout the project. Several model studies have used this template [61-64] in close collaboration with the project supervisor, [name].

ESTAIR is a psychotherapeutic manual for the treatment of CPTSD. It contains 25 sessions that are organized in 4 modules, targeting the CPTSD symptom categories. In addition to an introductory session, which include psychoeducational material, the manual contains three other modules to address the DSO symptoms clusters. The included modules are as follows: emotion regulation (5 sessions), self-concept (6 sessions), and relationship difficulties (5 sessions). Module 4 (5-7 sessions) is based on narrative reprocessing, which helps treat PTSD symptoms. Afterwards, there is one final session covering relapse prevention and a summary of the work. The manual concludes with a relapse prevention/closure session. Please find in Appendix 3 an overview of ESTAIR manual sessions.

The manual will be translated into Egyptian Arabic to facilitate use during therapy. After the final adjustments are made based on the pilot findings and patient feedback, the manual will be further modified accordingly.

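### Section 3.8 gives Module 4 as 5-7 sessions but says participants will be asked about 4, and ties the weekly peer-supervision meetings to an 18-week period that fits only the 3-module plan

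*Combined protocol and SAP*

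**What the plan says.** All references are to the combined protocol and SAP.

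**Length of Module 4**
- Section 3.4, on the manual: "Module 4 (5-7 sessions) is based on narrative reprocessing".
- Section 3.8, Therapeutic program: "Module 4 will take 5-7 sessions". The next sentence limits the module to 5-10 participants for budget reasons. The one after that says participants will be asked if they are "interested to conduct additional 4 sessions to enhance PTSD symptoms", one group at a time until enough have agreed.
- Section 3.8, 4-module table: the entry "Module 4 (individual therapy)" occupies weeks 18-24, with a final session in week 25 and post-assessment in week 26.
- Section 3.8, Screening & informed consent: participants are told of a "standardized group therapy following a manual that includes 18-25 sessions".

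**Period of the weekly meetings**
- Section 3.8, Supervision: "During the 18-week intervention, weekly preparatory and peer-supervision meetings will be held".
- Section 3.8, 3-module table: the final session is in week 18 and post-assessment in week 19.

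**The concern.** The figure of 4 appears where the plan describes how people will be asked to take on the individual trauma-narrative module, in the same paragraph that gives the module 5-7 sessions. Two things follow. The invitation may quote a shorter commitment than the rest of the protocol describes. And the end of Module 4 is not fixed: someone who attends four sessions has attended everything on one figure and only part on the other.

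The supervision sentence raises a separate point. An 18-week intervention describes the 3-module plan only. For the 5-10 people who go on to Module 4, therapy continues to week 25, and the sentence does not say whether the weekly preparatory and peer meetings continue with it.

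**Working it through.** **Inputs**
- Modules 1 to 3, section 3.4: "emotion regulation (5 sessions), self-concept (6 sessions), and relationship difficulties (5 sessions)".
- Introductory session, section 3.4: "In addition to an introductory session", counted as 1.
- Final session: 1. Section 3.4 mentions a closing session in two successive sentences, but each table in section 3.8 shows only one, so it is counted once.
- Module 4: 5-7 sessions (sections 3.4 and 3.8), or 4 (section 3.8, the question to participants).
- Weeks: the two tables in section 3.8.

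**Reproducing the plan's own totals**
- 3-module plan: 1 + 5 + 6 + 5 + 1 = 18. This matches the lower end of the 18-25 told to participants.
- 4-module plan with 7 sessions: 18 + 7 = 25. This matches the upper end of that range and the 25 sessions of the manual in section 3.4.
- 4-module plan with 5 sessions: 18 + 5 = 23.

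**Using the figure in the question to participants**
- 18 + 4 = 22. This lies inside the span 18-25 but is the length of neither plan: the 3-module plan has 18, and a 4-module plan with 5-7 sessions has 23-25.
- Difference from the other passages: 5 - 4 = 1 and 7 - 4 = 3, so 1 to 3 sessions. As a share of Module 4 this is 1/5 = 20% to 3/7 = 43%.
- Someone who attends four Module 4 sessions has attended 4/4 = 100% on one figure, and 4/7 = 57% to 4/5 = 80% on the other.
- Table slot: weeks 18 to 24 are 24 - 18 + 1 = 7 weeks, which accommodates 7 weekly sessions and does not suggest 4.

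**Weeks covered by the meeting sentence**
- 3-module plan: therapy in weeks 1-18, so 18 weeks. The sentence fits. It also agrees with the group-therapy calendar in section 10 (week of 18 August to week of 22 December, 18 weeks apart).
- 4-module plan: therapy in weeks 1-25, so 25 weeks. Weeks not addressed: 25 - 18 = 7 (weeks 19-25).
- Of those seven, weeks 19-24 are Module 4 (24 - 19 + 1 = 6 of its 7 weeks) and week 25 is the final session. The first Module 4 week, week 18, is inside the stated period.

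**The case against.** The strongest reply is that this is an editorial slip with little consequence. Much of that stands.

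- **Disclosure.** Participants hear of 18-25 sessions before they consent, and both 22 and 23-25 lie inside that range. A reader might infer that volunteers will knowingly be signed up for more than they agreed to. The documents do not show that: section 3.8 describes what will be asked but gives no script, and the consent forms are not available here. The disclosure is only a partial answer, because it speaks of group therapy while Module 4 is individual, and it does not say how long Module 4 is.
- **A possible misprint.** The 4 may have been meant as the module's number and not as a count of sessions. That is plausible but not shown, and the sentence as printed gives a count.
- **Primary outcome.** A reader might infer that the feasibility outcome has no agreed denominator. It has one: section 3.11 takes the percentage who complete the study among those who signed consent, so it counts people. That section also mentions adherence and the mean and standard deviation of completion rates, but it does not define either by session. The 57% to 80% above therefore illustrates Module 4 attendance and is not a feasibility result.
- **Model variable.** A reader might infer that the multilevel models are affected, because section 3.11 glosses group allocation as the number of sessions. The natural reading is an exploratory contrast of the 3-module and 4-module plans, which is the same whichever length Module 4 has.
- **Supervision.** A reader might infer that supervision stops when Module 4 begins. It does not. Module 4 begins in week 18, inside the stated period. Only the weekly preparatory and peer meetings are tied to 18 weeks. The weekly supervision of trainees and the twice-monthly team supervision in section 3.8 carry no end date, nor does the senior supervision promised in section 4.1. Sections 3.9 and 4.2 likewise refer risk cases to team supervision without a time limit.

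What the reply does not remove is the conflict between 4 and 5-7 in one paragraph, or the silence about the weekly peer meetings after week 18.

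**Conclusion.** Wrong as written; minor. The number of Module 4 sessions contradicts itself within section 3.8, and the 4 also conflicts with section 3.4 and the 4-module table. The size is 1 to 3 sessions, or a total of 22 against 23-25, for the 5-10 participants expected to take the module. The practical effects are a possibly understated invitation and an unclear end point for Module 4.

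Separately, the sentence on weekly preparatory and peer meetings does not address weeks 19-25 of the 4-module plan. Those meetings are unstated for seven weeks; they are not excluded, and supervision as a whole is not shown to lapse.

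The counts assume one introductory and one final session, which reproduces the plan's own 18 and 25. No significance level, power figure, sample size or primary-outcome definition changes. No view is taken on which session number or which supervision period is right.

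**What to change.** Before anyone is invited to Module 4:

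1. Reconcile the session number in the question to participants with sections 3.4 and 3.8 and the 4-module table, and carry the same number into the invitation.
2. State what counts as completing Module 4 in terms of the reconciled number. If that number remains a range, deleting the 4 will not settle this by itself.
3. Reconcile the stated period of the weekly preparatory and peer-supervision meetings with the 4-module schedule.

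The cost is a few lines of protocol and invitation wording, with whatever ethics notification section 4.4 requires. No analysis has to be redesigned.

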3.11. Data Analysis

Statistical analysis plan

For primary outcomes: We will primarily assess feasibility by determining the percentage of participants who complete the study until the end (among those who sign the informed consent). Based on reported dropout rates from studies using similar modular interventions with trauma survivors, we will consider 80-90% participation and adherence as excellent, 70-80% as satisfactory, and 60-70% as acceptable [42, 77].

We will assess the ITI feasibility, using the same method based on the percentage of participants who complete the ITI; 80-90% participation and adherence is considered as excellent, 70-80% as satisfactory, and 60-70% as acceptable.

In addition, we will calculate the mean and standard deviation of completion rates to offer more detail into the variation in adherence.

For secondary outcomes: Descriptive statistics will be calculated for demographic information and baseline characteristics of participants. For clinical outcomes, we will analyze changes in PTSD symptomatology and other clinical outcomes (e.g., depression, anxiety, somatic symptoms, and well-being) at the four or five measurement points depending on group allocation. (See section 3.8 procedures). We will use intermediate assessments after each module to statistically describe the participants' state (means, standard deviations, correlations), enhancing our understanding of the effects of intervention components.

Next, we will use pre-post comparisons based on data from the first and last assessments to establish the status of change (clinically significant change) for each participant. We will conduct one-

sided paired measures Student's t-tests at the group level. The null hypothesis (H0) is that the change is zero. The alternative hypothesis (H1) is there will be a decrease in symptoms of CPTSD, depression, anxiety, and somatization; and an increase in rates of wellbeing. Student's t tests will be conducted with a significance level of 0.05. If the assumptions for the Student's t test are not satisfied, we will utilize non-parametric tests, specifically the Wilcoxon test for paired measurements.

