We will perform longitudinal analyses utilizing multilevel linear models. This will enable us to gain a deeper understanding of how participants' progress throughout the duration of psychotherapy. The multilevel models will enable us to examine the impact of additional variables, such as gender, type of trauma, or group allocation (i.e., number of sessions), in an exploratory manner.

Considering our limited sample size of 20 participants and the fact that similar interventions have shown an effect size of 0.24, we acknowledge that the lack of statistical power may prevent us from observing the effects of our intervention on clinical outcomes.

Statistics will be conducted by the same team that conducted the analysis of the parallel Swiss arm of the study (see Section 3.2 Research Team) and will be facilitated by the free software R [78]

Qualitative analysis

We will use framework analysis to extract the most important information related to acceptability from patient and therapists qualitative interviews [79]. We will use MAXQDA software to facilitate analysis [80]. Data will be transcribed and translated in Arabic by the applicant and research assistants, who are native speakers.

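### The pre-post tests treat participants as independent although modules 1 to 3 are given in four therapy groups of five, so the 0.05 level is not assured

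*Combined protocol and SAP*

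**What the plan says.** **Delivery.** Section 3.8 gives modules 1 to 3 face to face in groups: "Participants will be divided into four groups" and "Each group will consist of five participants". Groups are formed by preferred location and/or shared characteristics such as gender or education, to help cohesion. Module 4 is individual, for 5 to 10 participants, and is offered to one group after another until the places are filled.

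**Pre-post tests.** Section 3.11 plans one-"sided paired measures Student's t-tests at the group level". "The null hypothesis (H0) is that the change is zero", and "Student's t tests will be conducted with a significance level of 0.05". If the assumptions fail, the fallback is non-parametric: "specifically the Wilcoxon test for paired measurements". Section 3.12 limits the analysis to participants with both assessments and does not impute.

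**Multilevel models.** "We will perform longitudinal analyses utilizing multilevel linear models". Their levels are not stated. The covariates to be explored are gender, type of trauma and group allocation, and the last is defined as number of sessions.

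**Limits the plan states itself.** Section 3.1 says that no efficacy conclusion can be drawn. Section 3.11 concedes low power: "Considering our limited sample size of 20 participants and the fact that similar interventions have shown an effect size of 0.24".

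**The concern.** The paired t-test takes its standard error from the spread of individual changes, as if each change were a separate piece of information. People treated together share sessions, group climate and the attendance of the others, so their changes may resemble each other. The number of sessions may also tend to follow therapy group, because module 4 is offered group by group. If changes are positively correlated within groups, the mean of 20 changes is less precise than the test assumes, and the test rejects too often when there is no change. The Wilcoxon test needs independent pairs too, so the fallback does not help.

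What is at stake is the calibration of the p-values for five clinical outcomes: CPTSD, depression, anxiety, somatic symptoms and well-being. Initial clinical impact is a stated aim (section 2), and a fully powered randomised trial is to follow (section 11). The low power that the plan admits is about missing effects. Excess false positives are a different problem, and the plan does not mention them.

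**Working it through.** **Inputs from the documents.** k = 4 groups, m = 5 per group, N = 20 (sections 3.6 and 3.8); one-sided level 0.05 (section 3.11); completers only (section 3.12). The lowest completion band called acceptable starts at 60%, which is 12 of 20, or m = 3 if losses are even.

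**Assumption.** The ICC of the change score, ρ, is not given. I use 0.05, 0.10 and 0.20, with 0 as reference.

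**Step 1: the plan's own figure.** With 20 independent changes, the critical value is t(0.95; 19 df) = 1.729 and the error is 0.0500. The stated level is reproduced.

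**Step 2: variance of the mean.** With σ the SD of change, Var(mean) = σ² × DE / N, where DE = 1 + (m − 1)ρ. For m = 5:
- ρ = 0.05: DE = 1 + 4 × 0.05 = 1.2; effective n = 20/1.2 = 16.7
- ρ = 0.10: DE = 1.4; effective n = 14.3
- ρ = 0.20: DE = 1.8; effective n = 11.1

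**Step 3: what the ordinary t-test uses instead.** Its sample variance follows (N − 1)S²/σ² = DE × χ²(3) + (1 − ρ) × χ²(16), independently of the mean. At ρ = 0.10 its expectation is (1.4 × 3 + 0.9 × 16)/19 = 18.6/19 = 0.979σ². The test therefore works with a variance of about 0.98σ²/20 where 1.4σ²/20 applies.

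**Step 4: actual one-sided error.** This is the average of 1 − Φ(t_crit × S/(σ√DE)) over the distribution of S², checked by simulating whole trials with zero true change.

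| Assumed ICC | t-test, 5 per group | t-test, 4 per group | t-test, 3 per group | Wilcoxon, 5 per group |
|---|---|---|---|---|
| 0 | 5.0% | 5.0% | 5.0% | about 5% |
| 0.05 | 6.6% | 6.2% | 5.8% | 6.5% |
| 0.10 | 8.2% | 7.5% | 6.6% | 7.9% |
| 0.20 | 11.1% | 9.8% | 8.4% | 10.8% |

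Separate runs agree to about 0.1 percentage point. At ρ = −0.05 with five per group, the t-test is conservative (3.4%).

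**Step 5: does a group-aware analysis restore the level?** A one-sided t-test on the four group mean changes (3 df) gave 4.9%, 5.2%, 5.0% and 5.2% at ρ = 0, 0.05, 0.10 and 0.20. A random therapy-group effect with Satterthwaite-type degrees of freedom gave 3.8% to 4.6%.

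**Step 6: its price at ρ = 0.10 with 20 completers.**
- Group means: SE = √(1.4/20) = 0.265 SD. With t(0.975; 3 df) = 3.182 this gives 0.842 SD. A sample SD on 3 df averages 0.921 of the true SD, so the expected 95% half-width is about 0.78 SD.
- Ordinary interval: 2.093 × √(0.979/20) = 0.46 SD.
- Power at a standardised change of 0.24 (the plan does not say what kind of effect size its 0.24 is): 18% for the group-mean test, against 27% for the ordinary t-test under independence.

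**The case against.** **The level may hold.** No ICC is given, and at zero the test is exact. A reader might infer that independence certainly fails and that the 0.05 level is certainly missed. The documents do not establish that. Section 3.8 does not assign therapists to groups, so a shared lead therapist cannot be assumed. Stable differences by location, gender or education cancel in change scores unless they also affect change. Shared group process remains a plausible source. This limits the claim to a level that is not assured.

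**The tests might already be on group means.** The group-level wording could be read so, and such a test would hold the level. But it stands in contrast to change for each participant in the sentence before. The completer rule and the power remark on 20 participants also point to participants as the unit. If four means were intended, the SAP should say so.

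**Multilevel models are planned.** They do not exclude a therapy-group level. They are, however, a separate analysis, do not name that level, and do not adjust the t-tests.

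**Little depends on these p-values.** This stands. The outcomes are secondary, the study is uncontrolled, efficacy conclusions are disclaimed, and no decision rule uses a p-value. Zero change is also a weak null in people selected for screening positive. A reader might go on to say that the reported confidence intervals will be too narrow, but section 3.11 specifies none.

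**The ICC is lost to the later trial.** A reader might infer this too. Four groups of five could not supply it: at a true ICC of 0.10 the between-group variance estimate is zero or below in about 40% of simulated trials, and the median 95% interval for the ICC runs from about −0.16 to 0.77.

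**Conclusion.** The point holds as a limited one. For any positive within-group correlation of change, the planned t and Wilcoxon tests exceed their stated level. For assumed ICCs of 0.05 to 0.20 the t-test error runs from 6.6% to 11.1% if all 20 complete, and from 5.8% to 8.4% if three per group do. These figures rest on the assumed ICC, groups of equal size and normally distributed changes. Nothing in the documents corrects for therapy group, and the multilevel section leaves it out by not specifying levels. The feasibility and acceptability results are not affected. The change is worth making because it is cheap and because choosing how to handle the groups after seeing the data would be less credible.

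**What to change.** In section 3.11:
- Name therapy group as a random effect in the planned multilevel model, with small-sample degrees of freedom (Satterthwaite type). It must act on change: a therapy-group effect on the time term, or a therapy-group intercept in a model for change scores. A group intercept on symptom level alone would not capture correlated change.
- Take the pre-post estimate and its 95% interval from that model.
- Show the t-interval on the four group mean changes (3 df) as a check. It is needed because the estimated group variance will often be zero, and the model then falls back to the ordinary analysis.
- Label the ordinary t and Wilcoxon p-values as unadjusted for therapy group and exploratory.
- Use separate terms for therapy group and for number of sessions.
- If an ICC is reported, give its interval and say that it is too imprecise to plan the randomised trial.

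**Cost.** SAP wording and one model term; recruitment, data collection and treatment do not change. Intervals become wider (about 0.78 SD against 0.46 SD half-width at ICC 0.10 with 20 completers), and power, already low, falls further.
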